8.4.4. Regulatory Reporting Requirements for SAEs

- Prompt notification by the investigator to GSK of an SAE is essential so that legal obligations and ethical responsibilities towards the safety of participants and the safety of a study intervention under clinical investigation are met.
- GSK has a legal responsibility to notify both the local regulatory authority and other regulatory agencies about the safety of a study intervention under clinical investigation. The Sponsor will comply with country-specific regulatory requirements relating to safety reporting to the regulatory authority, Institutional Review Boards (IRB)/Independent Ethics Committees (IEC), and investigators.
- An investigator who receives an investigator safety report describing an SAE or other specific safety information (e.g., summary or listing of SAEs) from GSK will review and then file it along with the IB and will notify the IRB/IEC, if appropriate according to local requirements.
- Investigator safety reports must be prepared for suspected unexpected serious adverse reactions (SUSAR) according to local regulatory requirements and GSK policy and forwarded to investigators as necessary.

8.4.5. Pregnancy

- Any female participant who becomes pregnant while participating in the study will not receive another dose of study intervention.
- Details of all pregnancies in female participants will be collected from the start of study intervention and until 30 weeks after the last administered dose of study intervention.
- If a pregnancy is reported, the investigator will record pregnancy information on the appropriate form and submit it to GSK within **24 hours** of learning of the female participant pregnancy. While pregnancy itself is not considered to be an AE or SAE, any pregnancy complication or elective termination of a pregnancy for medical reasons will be reported as an AE or SAE.
- Abnormal pregnancy outcomes (e.g., spontaneous abortion, foetal death, stillbirth, congenital anomalies, ectopic pregnancy) are considered SAEs and will be reported as such.
- The participant will be followed to determine the outcome of the pregnancy. The investigator will collect follow-up information on the participant and the neonate, and the information will be forwarded to the Sponsor.
- Any post-study pregnancy-related SAE considered reasonably related to the study intervention by the investigator will be reported to the Sponsor as described in Section 8.4.4. While the investigator is not obligated to actively seek this information in former study participants, he or she may learn of an SAE through spontaneous reporting.

8.4.6. Cardiovascular and Death Events

For any CV events detailed in [Appendix 3](#) and all deaths, whether or not they are considered SAEs, specific CV and Death sections of the CRF will be required to be completed. These sections include questions regarding CV (including sudden cardiac death) and non-CV death.

The CV CRF pages are presented as queries in response to reporting of certain CV MedDRA terms. The CV information should be recorded in the specific CV section of the CRF within one week of receipt of a CV Event data query prompting its completion.

The Death CRF page is provided immediately after the occurrence or outcome of death is reported. Initial and follow-up reports regarding death must be completed within one week of when the death is reported.

8.4.7. Adverse Events of Special Interest

Adverse events of special interest (AESI) include:

- Allergic reactions including anaphylaxis

Note: these events will be assessed by the investigator as to whether they meet the diagnostic criteria for anaphylaxis as outlined by the 2006 Joint NIAID/FAAN Second Symposium on Anaphylaxis [[Sampson, 2006](#)] ([Appendix 8](#)).

- Type III hypersensitivity (immune complex disease/vasculitis) reactions
- Local injection site reactions
- QTc prolongation

See Section [2.3.1](#) for additional details.

8.4.8. Medical Device Deficiencies

Medical devices (PFS) are being provided for use in this study as a delivery method for GSK3511294 or matching placebo injections. To fulfil regulatory reporting obligations worldwide, the investigator is responsible for the detection and documentation of events meeting the definitions of device deficiency that occur during the study with such devices.

The definition of a Medical Device Deficiency can be found in Section [10.7](#).

NOTE: Deficiencies fulfilling the definition of an AE/SAE will also follow the processes outlined in Section [10.3](#) of the protocol.

8.4.8.1. Time Period for Detecting Medical Device Deficiencies

- Medical device deficiencies that result in an incident will be detected, documented, and reported during all periods of the study in which the medical device is used.
- The method of documenting Medical Device Incidents is provided in Section [10.7](#).

8.4.8.2. Follow-up of Medical Device Deficiencies

- Follow-up applies to all participants, including those who discontinue study intervention or the study.
- The investigator is responsible for ensuring that follow-up includes any supplemental investigations as indicated to elucidate the nature and/or causality of the deficiency.
- New or updated information will be recorded on the originally completed form with all changes signed and dated by the investigator.

8.4.8.3. Prompt Reporting of Medical Device Deficiencies to Sponsor

- Device deficiencies will be reported to the Sponsor within 24 hours after the investigator determines that the event meets the protocol definition of a device deficiency.
- The Medical Device Deficiency Report Form will be sent to the Sponsor by email. If email is unavailable, then fax should be utilised.
- The Sponsor will be the contact for the receipt of device deficiency reports.

8.4.8.4. Regulatory Reporting Requirements for Medical Device Incidents

- The investigator will promptly report all deficiencies occurring with any medical device provided for use in the study in order for the Sponsor to fulfil the legal responsibility to notify appropriate regulatory authorities and other entities about certain safety information relating to medical devices being used in clinical studies.
- The investigator, or responsible person according to local requirements (e.g., the head of the medical institution), will comply with the applicable local regulatory requirements relating to the reporting of device deficiencies to the IRB/IEC.

8.5. Pharmacokinetics

- Blood samples will be collected for measurement of plasma concentrations of GSK3511294 as specified in the SoA (Section 1.3).
- The actual date and time (24-hour clock time) of each sample will be recorded. Samples obtained at Visit 2 (Week 0) and Visit 10 (Week 26) should be drawn prior to dosing.
- Collection, processing, storage and shipping procedures are provided in the central laboratory manual.
- Intervention concentration information that would unblind the study will not be reported to investigative sites or blinded personnel until the study has been unblinded.

8.6. Genetics and Pharmacogenomics

A blood sample for DNA isolation will be collected from participants who have consented to participate in the genetics analysis component of the study. Participation is optional. Participants who do not wish to participate in the genetic research may still participate in the study.

In the event of DNA extraction failure, a replacement genetic blood sample may be requested from the participant. Signed informed consent will be required to obtain a replacement sample unless it was included in the original consent.

See Section 10.5. Genetics and Pharmacogenomics for Information regarding genetic research. Details on processes for collection and shipment and destruction of these samples can be found in the central laboratory manual. Country specific requirements are specified in the SRM.

8.7. Biomarkers/ Pharmacodynamic Markers

8.7.1. Blood Eosinophil Counts

In order to investigate the PD effects of GSK3511294, blood eosinophil counts will be measured as part of the standard haematological assessments according to the SoA (Section 1.3). The site staff and central study team will be blinded to each participant's blood eosinophil count (as well as overall haematology differential [absolute and % values of eosinophils, lymphocytes, basophils, neutrophils, and monocytes]) from all post-randomisation blood tests. Total white blood cell counts will be available throughout the study.

8.7.2. Complement, IgE, and Inflammatory Markers

Blood samples will be collected to measure complement (C3 and C4) and total IgE, according to the SoA (Section 1.3).

A baseline serum sample will be collected at Visit 2 and stored. If necessary, this sample may be analysed for the presence of ANCA (using anti-MPO antibody and anti-PR3 antibody tests), and ANA, including anti-dsDNA antibodies. After dosing, additional inflammatory markers and tests may be considered on an ad-hoc basis should there be clinical concerns regarding an immune-mediated AE (see Section 7.5).

8.7.3. Exploratory Biomarkers

With the participant's consent and where permitted, a serum sample for exploratory biomarkers will be collected as specified in the SoA (Section 1.3). The samples will be stored after collection and may be analysed for any biomarkers that are thought to play a role in GSK3511294 response, asthma or related diseases, or to evaluate their association with observed clinical responses to GSK3511294. Samples may be stored for a maximum of 15 years (or according to local regulations) following the last participant's last visit for the study at a facility selected by the Sponsor to enable further analysis of biomarker responses to GSK3511294.

Participation in exploratory biomarker research is optional. Participants who do not wish to participate in the exploratory biomarker research may still participate in the study. Country specific requirements are specified in the SRM.

8.8. Immunogenicity Assessments

Antibodies to GSK3511294 will be evaluated in serum samples collected from participants according to the SoA (Section 1.3). Additionally, serum samples should also be collected at the Exit Visit or the final in-clinic visit for participants who withdraw early from the study. Processing, storage and shipping procedures are provided in the SRM.

In the immunogenicity assessment for GSK3511294, a tiered analyses approach will use a validated binding ADA assay (screening, confirmation and titration assays) and a validated neutralisation antibody (NAb) assay. If necessary, further immune response characterisation may be performed as needed.

8.9. Medical Resource Utilisation and Health Economics

Health Economics/Medical Resource Utilisation data, associated with medical encounters, will be collected by the investigator and study-site personnel for all participants throughout the study. The data will be collected using a medical problems and healthcare utilisation worksheet according to the SoA (Section 1.3). Protocol-mandated procedures, tests, and encounters are excluded.

The data collected may be used to evaluate the effect of GSK3511294 on health care resource utilisation for asthma including hospitalisation, ED visits, and physician office/clinic visits.

9. STATISTICAL CONSIDERATIONS

9.1. Statistical Hypotheses

The primary study objective is to test for the superiority of GSK3511294 100 mg SC + SoC following two doses (at Week 0 and at Week 26) compared with placebo + SoC, assessed by the annualised rate of clinically significant exacerbations measured over the study intervention period of 52 weeks.

The study will test at a 5% two-sided significance level the null hypothesis that there is no difference in annualised exacerbation rate between GSK3511294 and placebo.

9.2. Sample Size Determination

Approximately 540 participants with severe uncontrolled asthma with an eosinophilic phenotype will be screened to ensure the randomisation of 375 participants in a 2:1 ratio to GSK3511294 (n=250) and matching placebo (n=125).

9.2.1. Sample Size Assumptions

A sample size of 375 participants (2:1 GSK3511294 to placebo allocation ratio) is based on sufficient power to conclude superiority on primary and key secondary endpoints.

9.2.1.1. Primary Endpoint

The assumed true annualised rate of exacerbations in the placebo arm is 1.18. Based on an assumed true treatment difference of a 50% reduction in annualised exacerbation rate between GSK3511294 + SoC and placebo + SoC, a sample size of 375 randomised participants (250 to GSK3511294, 125 to placebo) will provide 99% power for the primary endpoint at a 5% two-sided significance level [[PASS](#), 2020].

The assumptions for the placebo rate and treatment effect are median values from an elicitation exercise which used Phase 3 anti-IL-5/5R historical data (~50% reduction in exacerbations) and expert opinion. The sample size is based also on an assumption of 0.8 for the dispersion parameter which was observed in two mepolizumab studies [[Pavord](#), 2012; [Ortega](#), 2014]. It was assumed that 14% of participant-years data will be missing due to study withdrawal, which is also consistent with mepolizumab studies.

Based on the assumptions above, the minimum observed treatment difference estimated to result in significance at the 5% two-sided significance level is a 27% reduction in exacerbations for GSK3511294 + SoC compared with placebo + SoC (rate ratio of 0.73).

9.2.1.2. Secondary Endpoints

[Table 3](#) describes the assumptions and power values for two key secondary endpoints. The assumptions are obtained from the Phase 3 mepolizumab studies [[Pavord](#), 2012; [Ortega](#), 2014; [Chupp](#), 2017].

Table 3 Power Calculations for Key Secondary Endpoints

Endpoint	Assumed treatment difference (GSK3511294 + SoC vs. placebo + SoC)	Standard deviation	Power
Change from baseline in SGRQ total score at Week 52	-7	17	96%
Change from baseline in ACQ-5 score at Week 52	-0.35	1.1	83%

9.2.2. Sample Size Sensitivity

The sample size and power calculations are based on assumptions about the true values for parameters. The power of the study is dependent on changes in these assumptions, in particular the assumed annualised exacerbation rates. Table 4 illustrates how changes in assumptions for two parameters (placebo + SoC annualised exacerbation rate and treatment effect) affect the power.

Table 4 Estimates of Power for Assumed Placebo + SoC Exacerbation Rate and Assumed Percent Reduction with GSK3511294 + SoC Compared with Placebo + SoC

Percent reduction in annualised exacerbation rate with GSK3511294 + SoC vs. placebo + SoC	Placebo + SoC annualised exacerbation rate			
	1.0	1.1	1.18	1.3
30%	61	63	65	67
40%	88	90	91	92
50%	98	99	99	99

9.3. Analysis Sets

For the purpose of analyses, the following populations are defined:

Population	Description
Screened	All participants who sign the ICF.
Enrolled	All participants who entered the study. Note screening failures (who never passed screening even if rescreened) and participants screened but never enrolled into the study (Met eligibility but not needed) are excluded from the Enrolled analysis set as they did not enter the study.

Randomised	All participants who were randomly assigned to study intervention in the study.
Full Analysis Set (FAS)	All randomised participants who receive at least one dose of study intervention. Participants will be analysed according to the intervention they are allocated at randomisation. This population will serve as the primary population for analyses of efficacy endpoints.
Safety	All randomised participants who receive at least one dose of study intervention. Participants will be analysed according to the intervention they are allocated at randomisation, unless a participant receives a different intervention to the randomised intervention at all protocol-defined administrations, in which case the participant will be analysed according to the actual intervention they received. This population will serve as the primary population for analyses of safety endpoints.

Further populations to be used for other assessments will be defined in the statistical analysis plan (SAP).

9.4. Statistical Analysis

The SAP will be finalised prior to un-blinding and it will include a more technical and detailed description of the statistical analyses described in this section.

This section is a summary of the planned statistical analyses of the most important endpoints including primary and key secondary endpoints.

9.4.1. General Considerations

The study will test at a 5% two-sided significance level the null hypothesis that there is no difference in annualised exacerbation rate between GSK3511294 + SoC and placebo + SoC.

9.4.2. Primary Endpoint

9.4.2.1. Main Estimand

Target Participant Population	Adult and adolescent participants with severe uncontrolled asthma with an eosinophilic phenotype following the strategy outlined below for dealing with the main intercurrent events that are anticipated.
Primary Endpoint	Annualised rate of clinically significant exacerbations over 52 weeks. Clinically significant exacerbations are defined in Section 8.2.2.
Intercurrent events and strategies	The anticipated key intercurrent events and corresponding strategies are: a) Study intervention discontinuation due to reasons unrelated to the COVID-19 pandemic: treatment policy strategy i.e. regardless of the intercurrent event occurring

	
b) Study intervention discontinuation due to reasons related to the COVID-19 pandemic: hypothetical strategy i.e. had the intercurrent event not occurred
 
c) Change in maintenance therapy or use of prohibited medications (listed in Section 6.9.2): treatment policy strategy i.e. regardless of the intercurrent event occurring

Summary measure	Ratio of the rates of exacerbations between GSK3511294 + SoC and placebo + SoC.
Analysis Method	The primary analysis of the annualised rate of clinically significant exacerbations will use a negative binomial model. Covariates included will be baseline maintenance OCS therapy (OCS vs. no OCS), baseline ICS dose (medium or high dose, see Appendix 10), region, number of exacerbations in the year prior to the study, baseline % predicted FEV ₁ and treatment group with log _e (time in study in years) as an offset variable. The rate ratio and 95% confidence interval (CI) will be provided for the comparison between GSK3511294 + SoC and placebo + SoC.
Handling of missing data and intercurrent events leading to exclusion of data	
Missing data or data excluded due to intercurrent events will be handled as follows:
 
 For participants that discontinue study intervention due to reasons related to the COVID-19 pandemic, the observed data for the period following this intercurrent event will be excluded from the analysis. Data for this period will be assumed “missing at random” (MAR) (based on all data included in the analysis under the current estimand strategy). For participants that withdraw from the study, preventing assessment of the primary endpoint, the data for the period following withdrawal will be assumed MAR (based on all data included in the analysis under the current estimand strategy). 
Sensitivity analyses will be conducted to investigate the conclusions from deviations from these assumptions regarding missing data for (b) above. Missing data for participants will be based on data from participants who have discontinued study intervention (off-treatment) but remained in the study [Roger, 2019]. A tipping point analysis will also be conducted that will impute missing data based on a plausible range of values for the rate of exacerbations per year. The imputed exacerbation rates will be varied independently for treatment arms. Further details will be provided in the SAP.

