4.3. Justification for Dose

The dose rationale for this study is supported by the FTIH Study 205722 [GlaxoSmithKline Document Number 2019N411063_00] that investigated single SC doses of GSK3511294 ranging from 2 mg to 300 mg. The FTIH study was designed to collect robust blood eosinophil pharmacology data (including washout) in a relevant population (mild to moderate asthma and a blood eosinophil count ≥ 200 cells/ μL at screening) and inform dose selection in late-phase development using Model-informed drug development (MIDD) principles [Wang, 2019; Marshall, 2019]. The precedence of using blood eosinophil reduction as a predictor of efficacy in severe asthma with an eosinophilic phenotype was established in two mepolizumab Phase 3 studies, which consistently reduced annualised exacerbation rate by approximately 50%, for associated reductions in blood eosinophils of 84% in the MENSA trial [Ortega, 2014] and 78% in the MUSCA trial [Chupp, 2017], compared with placebo. Since GSK3511294 targets the same IL-5 epitope as mepolizumab, establishing the same reduction in blood eosinophils

as mepolizumab via the same IL-5 neutralisation is expected to generate the same clinical efficacy in the same patient population (i.e., severe asthma with an eosinophilic phenotype with a previous history of two or more exacerbations in the past 12 months). In addition, given the precedented safety profile of IL-5 neutralisation comparable to placebo, targeting previous mepolizumab pharmacology is both valid and expeditious in selecting the dose of GSK3511294.

A comprehensive analysis of the clinical effects of GSK3511294 on blood eosinophils from Study 205722 was therefore conducted to identify the dose and frequency of dosing that match previous Phase 3 mepolizumab target pharmacology most closely. To this end, a Bayesian non-linear mixed-effects dose-time response model was used to analyse blood eosinophil data. This model was then used to calculate the posterior probability of achieving reductions of 78% for the MUSCA trial [Chupp, 2017] and 84% for the MENSA trial [Ortega, 2014] compared with placebo. Doses deemed suitable were defined as having a probability of exceeding MUSCA in excess of 80% while doses deemed unsuitable as having a probability of exceeding MENSA of less than 10%.

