4.2.3.2. Sensitivity Analysis 2 (Tipping Point Analysis)

Tipping point analysis will explore the impact of missing data by using differing assumptions regarding the exacerbation rate in subjects who withdraw from the study. Subjects who withdrew from study early will have missing data imputed for the period of time between withdrawal from the study to the Week 52 visit based on a range of values for the rate of exacerbations per year following study withdrawal. The values to be investigated will be based on increases relative to the estimated rates obtained within each arm under the MAR assumption. The imputed exacerbation rates will vary independently for the active and placebo arms, and will include scenarios where subjects in the active arm have worse outcomes following early withdrawal from the study than subjects in the placebo arm. The tipping point multiple imputation method will be based on pattern mixture models [Keene, 2014]. The results from the analyses of each sample are combined using Rubin's method.

If the test for the endpoint is not significant at the two-sided 5% level, then the sensitivity analysis for the endpoint will not be performed.

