4.3.4. Sensitivity analyses

The sensitivity analyses for the primary endpoint as described in Section 4.2.3 will also be performed for the secondary endpoints.

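### The SAP's tipping-point grid only raises rates above MAR, so the joint case of active withdrawers worse and placebo withdrawers better lies outside it; this matters only near the significance boundary

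*Protocol*

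**What the plan says.** For the primary endpoint, Protocol 9.4.2.1 commits to a tipping-point analysis that will "impute missing data based on a plausible range of values for the rate of exacerbations per year". It adds that "The imputed exacerbation rates will be varied independently for treatment arms" and that "Further details will be provided in the SAP". It gives no numerical range.

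SAP 4.2.3.2 supplies the rule: "The values to be investigated will be based on increases relative to the estimated rates obtained within each arm under the MAR assumption". It keeps separate variation ("The imputed exacerbation rates will vary independently for the active and placebo arms") and says that the scenarios will include active withdrawers doing worse after withdrawal than placebo withdrawers. It gives no maximum and no step size. The analysis is run only if the endpoint is significant.

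SAP 4.2.3.1 (Sensitivity Analysis 1) imputes from the off-treatment data of participants who stopped treatment but stayed in the study. It has no directional limit. It is skipped if less than 3% of study time is unobserved or excluded, or if less than half of the off-treatment period is observed.

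For the secondary endpoints, SAP 4.3.4 says only: "The sensitivity analyses for the primary endpoint as described in Section 4.2.3 will also be performed for the secondary endpoints". Protocol 9.4.3.1 promises a plausible range of means, varied by arm, for the continuous endpoints.

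**The concern.** A tipping-point analysis asks how far the missing data must depart from MAR before significance is lost, and whether that departure is believable. If the imputed rate may only rise in each arm, every step on the placebo axis favours the drug. On that axis the harshest value examined is MAR itself. Adverse departures can then enter only through the active arm, and the cells that combine active worse than MAR with placebo better than MAR are absent.

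That combination is plausible on the documents' own terms. The primary estimand puts "Change in maintenance therapy or use of prohibited medications (listed in Section 6.9.2): treatment policy strategy", and Section 6.9.2 lists the approved anti-IL-5/5R antibodies among the prohibited medicines. Protocol 4.3 says of two mepolizumab trials that treatment "which consistently reduced annualised exacerbation rate by approximately 50" percent. A placebo participant who left the study and started such a drug could have a lower rate than MAR predicts, and the estimand would count it. At stake is how a marginally significant result is read: the tipping scenario on display may look less believable than one that is not displayed.

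**Working it through.** **Inputs.** From Protocol 9.2.1.1 and SAP 5.1.1: 250 active and 125 placebo participants, placebo rate 1.18 per year, rate ratio 0.50, dispersion 0.8, 14% of participant-years missing (mean follow-up 0.86 years), two-sided 5%. Assumptions added here: the 14% applies equally to both arms, and the standard error (SE) stays at its MAR value instead of being re-estimated by Rubin's rules.

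**The plan's own figures.**

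Var(log RR) = 1/(0.86 × 1.18 × RR × 250) + 1/(0.86 × 1.18 × 125) + 0.8 × (1/250 + 1/125)

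At RR 0.50 this is 0.00788 + 0.00788 + 0.00960 = 0.02537, so SE = 0.159. Power = Φ(0.693/0.159 − 1.96) = 99.2%, against 99% stated. The largest significant rate ratio is exp(−1.96 × 0.159) = 0.732, against 0.73 stated. All 12 cells of the power table (Protocol Table 4, SAP Table 7) reproduce to within one point.

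**Direction on the placebo axis.** Let mA and mP multiply the MAR rate over the missing 14% in the active and placebo arms:

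RR* = RR × (0.86 + 0.14 mA)/(0.86 + 0.14 mP)

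From RR 0.50 with mA = 1, mP = 1.5 gives 0.50/1.07 = 0.467 and mP = 2 gives 0.50/1.14 = 0.439. Upward placebo steps move the ratio in the drug's favour.

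**Active multiplier at which significance is lost.**

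mA = {[exp(−1.96 SE)/RR] × (0.86 + 0.14 mP) − 0.86}/0.14, with SE taken at the MAR rate ratio shown.

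| MAR rate ratio | SE | Significance limit | mP = 1 | mP = 0.75 | mP = 0.5 |
|---|---|---|---|---|---|
| 0.50 | 0.159 | 0.732 | 4.31 | 3.95 | 3.58 |
| 0.60 | 0.155 | 0.738 | 2.64 | 2.33 | 2.03 |
| 0.65 | 0.153 | 0.740 | 1.99 | 1.71 | 1.42 |
| 0.70 | 0.152 | 0.742 | 1.43 | 1.17 | 0.90 |

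Only the mP = 1 column, and values above 1, are in the SAP's grid.

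**Reading the rows.**
- At 0.50, placebo × 0.5 alone gives 0.538 (95% CI 0.393 to 0.735). Even placebo × 0 gives 0.581 (0.425 to 0.794). Neither tips.
- At 0.65 with placebo at MAR, active withdrawers must reach 1.99 × 0.65 = 1.29 times the placebo MAR rate, which a reader could dismiss as worse than no drug. With placebo at 0.5 they need 1.42 × 0.65 = 0.92 times that rate, so losing the drug effect is enough.
- At 0.70, placebo × 0.5 alone gives 0.753 (0.559 to 1.014; p = 0.06). The result is lost with no worsening in the active arm.

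**Secondary endpoints.** The rule carried over by SAP 4.3.4 is stated in exacerbation rates. It transfers directly to the hospitalisation/ED rate. For FEV1 higher is better; for SGRQ, ACQ-5, ADSD and ANSD higher is worse. The SAP assigns no direction of shift to any of them.

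**The case against.** The strongest reply is that the adverse direction is already covered. SAP 4.2.3.2 commits to active withdrawers doing worse than placebo withdrawers and sets no upper limit on the active multiplier. Under the formula above, every cell with placebo below 1 has the same rate ratio as some cell with placebo at 1 and a larger active multiplier: placebo × 0.5 equals active × 1.54 (1/0.93 = 1.075; (1.075 − 0.86)/0.14 = 1.54). Active × 1.42 with placebo × 0.5 lies on the same boundary as active × 1.99 with placebo at MAR. This stands. What the grid lacks is the display of the joint case by which its plausibility would be judged.

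Other points also stand:
- Sensitivity Analysis 1 may pick up lower off-treatment placebo rates, so a reader who infers that placebo improvement is never examined goes too far. That holds for the tipping grid only, although Sensitivity Analysis 1 can be skipped.
- A multiplier of 0.5 assumes that every missing placebo person-year is spent on a fully effective anti-IL-5. The documents give no uptake figure, and active withdrawers could start the same drugs.
- At 0.70 the planned grid already shows fragility: it tips at 1.43, which is also the multiplier for reverting to the placebo rate (1/0.70).
- If the true ratio is 0.50 with SE 0.159, an observed ratio between 0.65 and 0.73 has a probability of only about 4%. It is less remote if the effect is smaller; the plan itself tabulates a 30% reduction, with 65% power.

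A reader might also infer that the SAP breaks a protocol promise. It does not: the protocol gave no numbers and left the detail to the SAP, which narrows the range but keeps variation by arm.

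**Conclusion.** The point holds in a limited form. As worded, SAP 4.2.3.2 excludes placebo multipliers below 1, so the corner with active worse and placebo better than MAR is outside the tipping grid. Taking the placebo multiplier to its 0.5 extreme lowers the active tipping multiplier by about 0.7 at rate ratio 0.50, where the conclusion stays robust. At 0.65 it falls from 2.0 to 1.4, and at 0.70 from 1.43 to 0.90. The omission therefore matters only for results near the 0.73 boundary. These sizes rest on equal 14% missingness by arm, placebo rate 1.18, dispersion 0.8 and an SE not re-estimated by multiple imputation.

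For the continuous secondary endpoints, a reader might infer that the rule would only ever improve missing FEV1 values. The documents do not support that: the increases in SAP 4.2.3.2 are in exacerbation rates, and Protocol 9.4.3.1 promises a range of means varied by arm. The fair criticism is that SAP 4.3.4 carries over a rate-based rule without stating a direction for these endpoints.

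**What to change.** In SAP 4.2.3.2, replace the restriction to increases with placebo multipliers on both sides of 1 (for example 0.5, 0.75, 1 and 1.25), crossed with active multipliers from 1 upward, and state the limits of the grid for each arm. Label 0.5 as the full-uptake extreme.

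In SAP 4.3.4, define the shifts for continuous endpoints by direction of outcome. Include active worse (lower FEV1; higher SGRQ, ACQ-5, ADSD and ANSD) together with placebo better.

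The cost is SAP wording and a few more cells in an analysis already planned. The downside is that the reported tipping point may look less favourable.
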